Rationale and background:	
The treatment of COPD increasingly involves multiple therapies, including long-acting bronchodilators (LAMAs and LABAs) and inhaled corticosteroids (ICS), with combinations of these drugs now formulated into single inhalers. The use of ICS has increased disproportionately with respect to COPD treatment guidelines and may be inappropriate in a subset of these users [P15-12888; P16-12287]. New evidence suggests that patients can be safely weaned off ICS, including the WISDOM trial that observed no difference in the risk of moderate or severe exacerbations between patients who discontinued ICS and those who continued receiving ICS [P14-13477]. Moreover, discontinuation of ICS has been associated with a reduction in the risk of pneumonia [P15-13167]. While most trials of the combination treatments have been conducted against the respective mono components or placebo, very few head-to-head trials versus other combinations have been performed to date. For example, the recent FLAME randomized trial reported that patients receiving the LABA-LAMA combination had fewer exacerbations than those receiving the LABA-ICS combination over a one-year follow-up period [P16-05628]. Also, the ENERGITO trial reported significant improvements in lung function with a LAMA/LABA combination versus LABA/ICS in GOLD 2-3 patients after 6 weeks of treatment [P16-01440]. These trials, however, represent a limited view of the patients who could potentially use these treatments, with many exclusion criteria based on for example stage of disease, lung function and exacerbation history, as well as exclusions of many patients during the screening and run-in periods. Thus, a real-world study of patients who are representative of clinical practice is of interest.
 
As many of these drugs have been in use in separate inhalers for many years, an observational study of their comparative effectiveness is feasible and would provide useful data on the relative benefits of these different combinations in the treatment of COPD. The intended audience is the scientific community, patients, payers and prescribers. The results from the study will be published in the scientific literature.
		

Name of company:	 Boehringer Ingelheim		
Boehringer Ingelheim			
Name of product:			
Spiriva			
Name of active ingredient:			
Tiotropium bromide			
Protocol date:	Study number:	Version/Revision:	Version/Revision date:
19 May 2017	0205-0538	1.1	Version 1.1, May 19, 2017
Proprietary confidential information			
© 2017 Boehringer Ingelheim International GmbH or one or more of its affiliated companies. All rights reserved.			
This document may not - in full or in part - be passed on, reproduced, published or otherwise used without prior written permission			
Research question and objectives:	
Primary: To assess the effectiveness of maintenance treatment of COPD with the combination of the LAMA tiotropium with a LABA compared with the combination of a LABA with ICS on the time to COPD exacerbation.
 
Secondary: To compare the effectiveness on the rate of exacerbation and the safety on the incidence of community acquired pneumonia for LABA and tiotropium with LABA and ICS.
		
Study design:	
A prevalent new-user cohort design will be used, with time-conditional propensity scores to match the two comparison groups.
		
Population:	
The base cohort will consist of all patients with a diagnosis of COPD who received at least one prescription for a long-acting bronchodilator, either LABA or the LAMA tiotropium, or for an inhaled corticosteroid from 1 January 2002 until 31 December 2015. To increase the likelihood of a diagnosis of COPD, we only include patients 55 years of age or older on the date of this initial prescription and exclude all patients with a prior diagnosis of asthma.
 
The primary study cohort will first be defined as the members of the base cohort with their first concurrent prescriptions of a LABA and tiotropium on the same date. Patients initiating a LABA and tiotropium will not include users of a LABA+ICS fixed dose combined inhaler.
 
Patients receiving for the first time a LABA and tiotropium on the same day will be propensity score and time matched with members of the base cohort who initiate treatment with LABA and ICS on the same day, either as a fixed-dose combination or free combination.
 
Subjects will need to have at least one year of medical history information prior to the date of combined treatment initiation (cohort entry date) to allow the identification of new use and the measurement of baseline covariates. Subjects will be followed for up to one year from the date of combined treatment initiation, or until switching to the other treatment, the date of death, 31 December 2016, or the end of coverage in the practice, whichever occurs first.
		
Study data source:	
United Kingdom's Clinical Practice Research Datalink (CPRD) linked with the Hospital Episodes Statistics (HES) database
		
Expected study size:	
New users of LABA and tiotropium : 3,000
 
New users of LABA and ICS: 3,000
		
Main criteria for inclusion:	
 - New users of long-acting bronchodilators, LABA and tiotropium on the same date or of LABA and ICS, either as a fixed-dose combination or free combination, on the same date between January 2002 and December 2015. - Diagnosis of COPD and age \geq 55 years 		

Name of company: Boehringer Ingelheim		 Boehringer Ingelheim	
Name of product: Spiriva			
Name of active ingredient: Tiotropium bromide			
Protocol date: 19 May 2017	Study number: 0205-0538	Version/Revision: 1.1	Version/Revision date: Version 1.1, May 19, 2017

Proprietary confidential information © 2017 Boehringer Ingelheim International GmbH or one or more of its affiliated companies. All rights reserved. This document may not - in full or in part - be passed on, reproduced, published or otherwise used without prior written permission
			
Main criteria for exclusion:	-Less than one year of medical history information prior to the date of combined treatment initiation (cohort entry) -Asthma diagnosis		
Comparison groups:	Initiating LABA and tiotropium compared to initiating LABA and ICS therapy		
Expected duration of exposure:	One year for the primary and secondary analyses		

TABLE OF CONTENTS

TITLE PAGE	1
PROTOCOL ABSTRACT	3
TABLE OF CONTENTS	6
LIST OF TABLES	8
LIST OF FIGURES	9
1. LIST OF ABBREVIATIONS AND TERMS	10
2. RESPONSIBLE PARTIES	11
3. AMENDMENTS AND UPDATES	12
4. MILESTONES	13
5. RATIONALE AND BACKGROUND	14
6. RESEARCH QUESTIONS AND OBJECTIVES	15
7. RESEARCH METHODS	16
7.1 STUDY DESIGN.....	16
7.2 SETTING.....	16
7.3 SUBJECTS	16
7.4 VARIABLES	17
7.4.1 EXPOSURES.....	17
7.4.2 OUTCOME(S).....	17
7.4.2.1 PRIMARY OUTCOME(S).....	17
7.4.2.2 SECONDARY OUTCOME(S).....	18
.....	18
7.4.3 COVARIATES.....	18
7.5 DATA SOURCES	19
7.6 BIAS	19
7.7 STUDY SIZE	19
7.8 DATA MANAGEMENT	20
7.9 DATA ANALYSIS	20
7.9.1 MAIN ANALYSIS	20
.....	21
7.10 QUALITY CONTROL.....	22
7.11 LIMITATIONS OF THE RESEARCH METHODS	22
7.12 OTHER ASPECTS	22
8. PROTECTION OF HUMAN SUBJECTS	23
9. MANAGEMENT AND REPORTING OF ADVERSE EVENTS/ADVERSE REACTIONS.....	24
10. PLANS FOR DISSEMINATING AND COMMUNICATING STUDY RESULTS	25
11. REFERENCES.....	26

11.1	PUBLISHED REFERENCES.....	26

1. LIST OF ABBREVIATIONS AND TERMS ---

AE	Adverse Event
BI	Boehringer Ingelheim
CI	Confidence Interval
COPD	Chronic obstructive pulmonary disease
CPRD	Clinical Practice Research Datalink
ICS	Inhaled corticosteroids
IR	Incidence Rate
LABA	Long-acting beta2-agonist
N	Number
PS	Propensity score
PSTAT	Project Statistician
PY	Person-years at risk
RR	Rate Ratio
TM Epi	Team Member Epidemiology
UTS	Up-to-standard

3. AMENDMENTS AND UPDATES

There are currently no amendments to the protocol.

4. MILESTONES

Milestone	Planned date
Start of data collection: Data extraction and coding	June 1, 2017
End of data collection:	Not applicable. This study is an observational study based on existing data.
Study progress report(s) as referred in Article 107m(5) of Directive 2001/83/EC:	tbd
Interim report(s) of study results:	Preliminary results: 30 December 2017
Registration in the EU PAS register	tbd
Final report of study results:	May 2018

5. RATIONALE AND BACKGROUND

Chronic obstructive pulmonary disease (COPD) is a leading cause of morbidity and mortality throughout the world [P07-11503]. It has recently risen to become the third leading cause of death in the US [R13-1383; minion et al. 2010]. Long-acting bronchodilator medications, that include long-acting beta₂-agonists (LABAs) and the long-acting muscarinic antagonists (LAMAs) such as the anticholinergic tiotropium, have become central maintenance therapy to the management of COPD, with inhaled corticosteroids (ICS) added with increasing severity[P07-11503].

As a result, the treatment of COPD increasingly involves using several of these drugs, with some of their combinations now formulated into single inhalers. The use of ICS has, however, increased disproportionately with respect to COPD treatment guidelines and may be inappropriate in a subset of patients, with new evidence suggesting that patients can be safely weaned off ICS.[P15-12888; P16-12287] Indeed, the large WISDOM trial observed no difference in the risk of moderate or severe exacerbations between patients who discontinued ICS and those who continued receiving ICS, while the OPTIMO study also observed no deterioration of lung function, symptoms, and exacerbation rate after withdrawal [P14-13477; P14-13078]. Moreover, discontinuation of ICS has been associated with a reduction in the risk of pneumonia [P15-13167]. While most trials of the combination treatments have been conducted against the respective mono components or placebo, few head-to-head trials versus other combinations have been performed to date. For example, the recent FLAME randomized trial reported that patients receiving the LABA-LAMA combination had fewer exacerbations than those receiving the LABA-ICS combination over a one-year follow-up period [P16-05628]. Similarly, the ENERGITO trial reported significant improvements in lung function with a LABA/LAMA combination versus LABA/ICS in GOLD 2-3 patients after 6 weeks of treatment [P16-01440].

These trials, however, were limited by the fact that a majority of the patients were already using these treatments that they had to discontinue and enter a run-in period before randomisation, which does not emulate the clinical setting. Moreover, the trials represent a limited view of the patients who could potentially use these treatments, with several exclusion criteria involving for example stage of disease, lung function and exacerbation history, in addition to the exclusions of many patients during the screening and run-in periods. Thus, a real-world study of patients who are representative of clinical practice is of interest. Finally, assessing the effectiveness in terms of COPD exacerbations should be balanced against the safety of ICS with respect to pneumonia in the context of real-world clinical practice.

6. RESEARCH QUESTIONS AND OBJECTIVES

The primary objective of this study is to assess the effectiveness of maintenance treatment of COPD with the combination of a LABA and the LAMA tiotropium (LABA-TIO) compared with the combination of a LABA and an ICS (LABA-ICS) on the time to COPD exacerbation. More specifically, the patients who initiate treatment with a combination of a LABA and tiotropium at the same time, or who are on a LABA (no ICS) and who add tiotropium, or who are on tiotropium and add a LABA (no ICS), will be compared with similar patients who receive a LABA and an ICS on the time to first COPD exacerbation.

The secondary objective is to assess the comparative effectiveness on the rate of exacerbation and the comparative safety on the incidence of community acquired pneumonia.

7. RESEARCH METHODS

7.1 STUDY DESIGN

Population-based propensity score-matched new-user cohort study.

7.2 SETTING

The study will be conducted in a general practice setting, within the United Kingdom's Clinical Practice Research Datalink (CPRD; details in Section 7.5). It will be restricted to the practices which can be linked to the Hospital Episodes Statistics (HES) database. The maximal observation period will be from January 1995 until December 2016.

7.3 SUBJECTS

The base cohort will consist of all patients with a diagnosis of COPD from 1 January 1995 until 31 December 2015 who subsequently received at least one prescription for a long-acting bronchodilator, either LABA or tiotropium, or for an inhaled corticosteroid, alone or in combination, from 1 January 2002 until 31 December 2015. The time span for the study was selected to ensure that LABAs and tiotropium were concurrently available, in view of the differing dates of market entry for LABAs (1990s) and tiotropium (2002). To increase the likelihood of a diagnosis of COPD, we will exclude all patients less than 55 years of age on the date of their initial prescription for these drugs during this time period and exclude all patients with a previous diagnosis of asthma. Because the definition of some outcomes under study involve hospitalization, the base cohort will be restricted to the practices which can be linked to the Hospital Episodes Statistics (HES) database (please refer to section 7.5).

Study Cohort

The study cohort will be formed from the base cohort using an incident new-user cohort design with time-conditional propensity scores [P17-04653]. We will thus identify from the base cohort all subjects who, during follow-up, received for the first time prescriptions for a LABA and a tiotropium on the same day, but no inhaled corticosteroid. This can occur as the first time they received a long-acting bronchodilator, with both a LABA and tiotropium as initial treatment, or with initial treatment with a single long-acting bronchodilator followed by the addition of the other long-acting bronchodilator. We will then identify from the base cohort all subjects who, during follow-up, received for the first time prescriptions for a LABA and an ICS on the same day, as two different prescriptions or in a single inhaler, but no tiotropium. Here again, this can occur as the first time they received a LABA and ICS as initial treatment, or with initial treatment with a LABA followed by the addition of ICS or vice versa. Cohort entry will be taken as the first date that LABA and tiotropium or LABA and ICS prescriptions are given simultaneously. All subjects will require at least one year of up-to-standard (UTS) medical history prior to study cohort entry to allow a baseline period for the covariates and identification of new use. New use will thus be defined as the first simultaneous prescriptions for LABA and tiotropium or for LABA and ICS, preceded by prescriptions for only one of the two drug classes or none in the baseline year.

To form the study cohort, we will identify, for each subject initiating LABA and tiotropium (LABA-TIO) treatment, a matched LABA-ICS comparator subject using a time-conditional

propensity score-matched approach. The potential comparator subjects will be selected from the base cohort by forming time-based exposure sets defined by the calendar year of entry into the base cohort for the LABA-TIO and LABA-ICS simultaneous prescription users. To allow matching on the propensity of treatment choice, we will compute high-dimensional time-conditional propensity scores (TCPS) by identifying all available data (e.g., diagnoses, procedures, medications) in the one-year period prior to the date of cohort entry for each time-based exposure set using Cox proportional hazards regression. Then, for each LABA-TIO exposed subject, and starting chronologically with the first one, we will identify a matched comparator subject from the members of the subject's time-based exposure set. We will first match subjects on sex, previous components of the study treatment (LABA only, TIO only, ICS alone, none of these) and the presence of an acute COPD exacerbation in the year before cohort entry. The matched reference subject will then be selected as the one with the closest time-conditional propensity score in the matched set, after trimming within each exposure set, and allowing a maximum difference in scores of 0.05 for a match. In the absence of a tight propensity score match, we will take the closest and the analysis will be complemented by an adjustment for the propensity score.

After matching, the subjects in the study cohort will be followed up for up to one year from cohort entry (the date of the matched set), with follow-up ending at the earliest of the date of a switch or addition of either an ICS for the LABA-TIO group or of tiotropium to the LABA-ICS group, death, one year after cohort entry, December 31, 2016, or the end of coverage in the practice, whichever occurs first.

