7.4 VARIABLES

7.4.1 EXPOSURES

The exposure measures are based on the prescription of the two long-acting bronchodilators under study, namely LABAs and tiotropium, as well as ICS. As described in the data analysis section, the as-treated analysis, which is the main analysis, will consider exposure as current use of LABA-TIO or LABA-ICS within the treated groups defined as within the 60-day period after the prescriptions' dispensing dates.

[figure not shown]

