7.4.2 OUTCOME(S)

7.4.2.1 PRIMARY OUTCOME(S)

The primary outcome event is the first COPD exacerbation to occur after cohort entry. The event is defined as a hospitalization for COPD (severe exacerbation) or the prescription of an oral corticosteroid, namely prednisolone (moderate exacerbation).

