7.4.3 COVARIATES

Sex, previous treatment and previous acute COPD exacerbation, as well as calendar year of cohort entry, are all matching factors and will thus inherently be accounted for.

Although we will use the high-dimensional approach to identify variables entering the time-conditional propensity score, some key covariates will be highlighted. First, we will identify key lifestyle variables available in the CPRD, known to be risk factors and potential confounders, including the body mass index (BMI), smoking status and excessive alcohol consumption. Missing data for smoking status and BMI will be entered as an additional category in the model. We will also explore the possibility of obtaining blood eosinophils measured in the year prior to cohort entry and will use this information only if complete.

Second, the occurrence of the study outcomes prior to cohort entry will be identified during the one-year baseline period and adjusted for in the analysis if found to be imbalanced between treatment groups after propensity score matching. In particular, COPD exacerbations occurring in the 30 days prior to the study cohort entry date, a marker of COPD exacerbation risk, will be identified separately from those occurring previously during the baseline year. In addition, the severe exacerbations requiring hospitalizations will be counted, while the moderate exacerbations will be identified from counts of prescriptions for oral corticosteroids.

Third, use of other respiratory drugs during the baseline period will be included as a measure of COPD severity. Thus, the number of prescriptions for short-acting beta-agonists, anticholinergics, methylxanthines and muscarinic antagonists used during the year prior to cohort entry will be identified. As well, the number of prescriptions for antibiotics for a respiratory condition will be counted. In addition, we will count the number of prescriptions for the study drugs used during the baseline period. These will be combined into a single variable because of the study design which inherently selects patients into the two study groups according to their prior LABA, TIO or ICS use. Finally, for each of the cohorts, baseline co-morbidity will be measured using diagnoses and prescriptions for various conditions observed often in patients with COPD, namely cardiovascular disease, diabetes, thyroid disease, renal failure, autoimmune disease and cancer, all in the year prior to cohort entry.

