7.9 DATA ANALYSIS

7.9.1 MAIN ANALYSIS

For the base cohort, patient characteristics at baseline will be described using standard descriptive statistics. The unmatched study cohort, which will also address the tertiary objective, will be used to provide and compare baseline patient characteristics between the two groups. These comparisons will also be provided for the matched cohort.

For the analysis of the primary objective, the matched cohort will be used to estimate the crude 1-year cumulative incidence of severe and moderate COPD exacerbations for the two combination treatment groups. The main comparative analysis will also be based on the matched cohort and a time-dependent Cox proportional hazard regression model to perform an as-treated analysis that assesses the effect of current use of LABA-TIO combination versus the LABA-ICS combination on the risk of a first COPD exacerbation. It will provide an estimate of the hazard ratio (HR) of a COPD exacerbation associated with LABA-TIO use relative to LABA-ICS use, along with 95% confidence intervals (CI). Current use will be defined as a prescription dispensed within the 60-day period of the date defined by the risk set of the Cox model. This approach allows consideration of exposure as time-dependent, accounting for the changes in exposure during the follow-up. In particular, this analysis

censors patients stopping one or both of the drugs prior to the index date. Besides the matching inherent in the design, the Cox proportional hazard regression model will be adjusted for additional confounders. This model will include patient characteristics found to be different after matching on propensity scores, as well as the decile of propensity score. Body mass index (BMI) is expected to be the only variable with missing data in the CPRD, though infrequently (less than 4% of subjects in our previous studies in COPD). Patients with missing BMI will be classified as a separate category.

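### Section 7.3 excludes and censors the LABA-TIO arm on any ICS but the LABA-ICS arm on tiotropium only, so comparator time with another LAMA added is counted as dual therapy; size unknown, probably small, direction open

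*Combined protocol and SAP*

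**What the plan says.** Section 7.3 sets the entry rules. The LABA-TIO arm is made up of patients who "received for the first time prescriptions for a LABA and a tiotropium on the same day, but no inhaled corticosteroid". The LABA-ICS arm is made up of patients who first received a LABA and an ICS "on the same day, as two different prescriptions or in a single inhaler, but no tiotropium". The end-of-follow-up rule in 7.3 keeps the same pairing: follow-up ends at "a switch or addition of either an ICS for the LABA-TIO group or of tiotropium to the LABA-ICS group", or at death, one year, the end of 2016 or the end of practice coverage.

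The as-treated analysis in 7.9.1 adds one more rule: it "censors patients stopping one or both of the drugs prior to the index date". Section 7.4.1 builds exposure on "the two long-acting bronchodilators under study, namely LABAs and tiotropium, as well as ICS".

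Section 5 describes the class more widely than the single drug: "long-acting muscarinic antagonists (LAMAs) such as the anticholinergic tiotropium". The LABA-LAMA versus LABA-ICS trial cited there appears in section 11.1 under a title that names indacaterol and glycopyrronium, so the LAMA in that trial was not tiotropium.

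The abstract is worded more narrowly than 7.3. It bars only users of a fixed-dose LABA+ICS inhaler from the LABA-TIO arm, and section 7.7 counts the arm in the same way. The abstract also ends follow-up on switching to the other treatment and does not mention additions.

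**The concern.** The primary objective compares two dual therapies. The plan accepts that a third maintenance drug ends valid follow-up, and it applies that principle in both arms. In the LABA-TIO arm the third drug is a whole class (ICS); in the LABA-ICS arm it is one agent of a class (tiotropium among LAMAs). A comparator patient on LABA+ICS plus another LAMA is on LABA+LAMA+ICS but is analysed as LABA-ICS.

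What is at stake is the meaning of the comparator and, to an unknown degree, the hazard ratio. For the primary analysis ("The primary outcome event is the first COPD exacerbation to occur after cohort entry") only use before the first exacerbation counts. For the one-year exacerbation rate in 7.4.2.2, use that starts after a first exacerbation counts as well.

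**Working it through.** **Step 1. Does any visible rule remove this time?** Take a LABA-ICS patient who renews both drugs and takes another LAMA.

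- Entry rule, 7.3: bars tiotropium only. Patient admitted.
- End-of-follow-up rule, 7.3: triggered by tiotropium only. Not triggered.
- As-treated censoring, 7.9.1: triggered by stopping the LABA or the ICS. Neither is stopped.
- Abstract: triggered by a switch to the other treatment, which for this arm is LABA and tiotropium. Not triggered.
- New-use definition, 7.3: for this arm it concerns LABA and ICS. Silent on other LAMAs.
- Prior-treatment matching, 7.3: the categories are LABA, tiotropium, ICS or none. There is none for another LAMA.
- Propensity score, 7.3, and baseline counts, 7.4.3 ("muscarinic antagonists used during the year prior to cohort entry will be identified"): these may balance use in the year before entry. They exclude and censor nobody and cannot reflect use that starts later.

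So the time stays in the comparator.

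**Step 2. How large could the effect be?** The plan gives no figure to reproduce on this point. Let s be the share of LABA-ICS person-time before the first event spent on LABA+LAMA+ICS, and r the hazard ratio of triple therapy against LABA-ICS alone. Both are assumptions. With hazards and s taken as constant, the comparator's average hazard is multiplied by (1 − s) + s·r, so

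reported HR = true HR / (1 − s(1 − r)).

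Multiplying factor on the LABA-TIO versus LABA-ICS hazard ratio:

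| s | r = 0.7 | r = 0.8 | r = 0.9 | r = 1.0 | r = 1.2 |
|---|---|---|---|---|---|
| 1% | 1.003 | 1.002 | 1.001 | 1.000 | 0.998 |
| 5% | 1.015 | 1.010 | 1.005 | 1.000 | 0.990 |
| 10% | 1.031 | 1.020 | 1.010 | 1.000 | 0.980 |
| 20% | 1.064 | 1.042 | 1.020 | 1.000 | 0.962 |

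At s = 10%, a true 0.90 would read 0.90/0.98 = 0.918 if r = 0.8, 0.900 if r = 1.0, and 0.90/1.02 = 0.882 if r = 1.2.

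**Step 3. Scale against precision.** Section 7.7 expects 3,000 patients per arm and a 50% one-year incidence, so about 0.5 × 6,000 = 3,000 first events. This is an upper figure, because it ignores as-treated censoring.

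- SE(log HR) = 2/√3000 = 0.0365.
- 95% CI half-width on the log scale = 1.96 × 0.0365 = 0.0716, about 7% on the hazard ratio.
- Shift at s = 10%, r = 0.8: ln(1.0204)/0.0716 = 0.28 of the half-width.
- With an assumed 2,000 events the half-width is 1.96 × 2/√2000 = 0.0877 and the fraction falls to about 0.23.
- Share needed for a shift equal to the half-width: (1 − e^(−0.0716))/(1 − r) = 69%, 35% or 23% for r = 0.9, 0.8 or 0.7.

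**The case against.** **No evidence of frequency.** Section 7.3 sets the window (entry 2002 to 2015) by the availability of LABAs and tiotropium. No passage shows how often, or when, other LAMAs were prescribed in this population. A class phrase and a trial title are not prescribing data. This stands, and it means that no size can be claimed.

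**Direction.** A reader might infer that triple therapy in the comparator dilutes the contrast and pulls the hazard ratio towards 1. The documents do not support that. The shift reverses if r exceeds 1, as it could if another LAMA is added when a patient is worsening. Even with r below 1, the same factor of 1.02 moves a true 1.00 to 1.02 and a true 1.10 to 1.12, away from the null.

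**Partly handled.** A reader might also infer that the plan ignores other LAMAs altogether. It does not: use before entry is open to balance through the propensity score and the 7.4.3 counts. A patient who drops the ICS for another LAMA is censored under 7.9.1. The gap is confined to patients who keep both drugs.

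**The rule being mirrored is not uniform.** The any-ICS exclusion is 7.3 wording; the abstract and 7.7 name only a fixed-dose LABA+ICS inhaler, and ICS alone is a prior-treatment category in 7.3. This stands as a reason to reconcile the passages. It does not remove the asymmetry within 7.3.

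**Shorthand.** Section 7.3 calls the components of each pair drug classes, and the code list is still open, so tiotropium may be meant to stand for its class. The text does not settle this. If so, the change below is a clarification only.

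**Tiotropium-specific question.** Ending follow-up at crossover to the other study component fits a question about tiotropium. That explains the definition of the treated arm; it gives no reason for a LABA-ICS comparator to admit other LAMAs.

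**Text not shown.** The 7.4.1 figure is missing, the contents list has blank entries after 7.4.2.2 and 7.9.1, and 7.9.1 refers to a tertiary objective that is not visible. A related analysis may exist there.

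**Conclusion.** The point holds as a definitional asymmetry in the visible text of 7.3. Among third drugs, only tiotropium excludes or censors a LABA-ICS patient, so continuing LABA and ICS with another LAMA is classed as dual therapy. Use before entry may be balanced; use starting at or after entry is not handled.

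Its size is unknown and probably small. At an assumed 10% share the factor on the hazard ratio is about 1.02, 1.00 or 0.98 for r = 0.8, 1.0 or 1.2, and at r = 0.8 the shift is about 0.28 of the confidence-interval half-width implied by 7.7. All of this rests on assumed values of s and r. A reader might infer that the primary result would be materially biased, or biased in a known direction. The documents support neither, because they give no frequency of other-LAMA use and no triple-versus-dual hazard ratio. It is a minor correction to make before the drug codes are fixed.

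**What to change.** - In 7.3, in both the LABA-ICS entry exclusion and its end-of-follow-up rule, replace tiotropium by any LAMA, alone or in a fixed combination.
- Add the other LAMAs to 7.4.1 and to the Annex 3.1 code list, which the protocol says is still to be finalised.
- Align the abstract with 7.3, both on ICS exclusion in the LABA-TIO arm and on additions as well as switches; reconcile the matching sentence in 7.7.
- If other LAMAs are meant to be allowed in the comparator, say so, give the reason, and describe the comparator accordingly.

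The cost is a longer code list and slightly more censoring in the LABA-ICS arm. That censoring may be informative, since a LAMA may be added when symptoms worsen, but it is of the kind the plan already applies to added ICS and tiotropium. If it removed 10% of the comparator's expected 1,500 events (an assumption), 2,850 events would remain and the half-width would go from 0.0716 to 1.96 × 2/√2850 = 0.0734. With over 100,000 LABA-ICS users in the pool (7.7), loss of matches is unlikely.
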